3.1.2 Secondary Objectives

1. To determine the safety and tolerability of pomalidomide for the treatment of HHT.
2. To determine if pomalidomide treatment improves quality of life in HHT.
3. To determine whether a continued response to pomalidomide is evident 4 weeks after treatment discontinuation.
4. To develop a biorepository for future studies to define biomarkers predictive of pomalidomide response and allow investigations into the biology of HHT and mechanisms of pomalidomide.

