3.2.4 Exploratory Outcomes

1. Rate of relapse at the 4-week post-treatment follow-up visit, where relapse is defined as a return of the ESS to the baseline value or greater in pomalidomide (or placebo)-treated subjects.
2. Median time after initiation of pomalidomide to obtain a decrease in the ESS of at least 1.0 in the in pomalidomide-treated subjects compared to placebo.
3. Effect of genotype on the response to pomalidomide.

Outcome Modification History:

The protocol originally specified that the PROMIS® Satisfaction with Social Roles and Activities Short Form 8a (V2.0) was to be the 3rd key secondary outcome. Part-way through the study (summer 2022) it was determined that due to an inadvertent error, the CRF meant to collect the PROMIS instrument instead corresponded to the Neuro-QoL™ Short form V 1.1 instrument with the same name, number of items, and response categories, but different items. As the study was over 50% enrolled when this issue was identified, the decision was made to update the protocol to specify the Neuro-QoL instrument instead of the PROMIS instrument. This update was made in Protocol version 2.10.

Although developed as part of an assessment system for people with neurological conditions, the NeuroQoL Satisfaction with Social Roles and Activities is scored relative to a general population sample (Gershon et al 2012), supporting its use in non-neurologic health conditions. For both the PROMIS and Neuro-QoL instruments, a T-score of 50 represents the average for the United States general population with a standard deviation of 10, and calibration testing was performed on a large sample of the general population. PROMIS was developed in 2016. Neuro-QoL was developed in 2014, and the T-score calculations are based on a normative population of over 5,000 individuals. The protocol was initially designed with a 12-week follow-up period, which was modified to a 4-week period in Protocol version 2.8 (August 2, 2021). Prior to the change, 20 participants had completed the 12-week rather than 4-week follow-up.

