9 EFFICACY ANALYSES

9.1 Overview of Efficacy Analysis Methods

- All efficacy analyses will be performed on the mITT population, the primary population.
- All efficacy variables will be summarized by treatment group at baseline and at subsequent study time points at which assessments were administered and collected. Count (N), mean, standard deviation, minimum, and maximum will summarize continuous efficacy variables, whereas number and percent will summarize categorical efficacy variables.
- Unless otherwise noted, all analyses of dichotomous outcomes, measured at respective time points, will be performed using models as specified in Section 9.3. Efficacy models will be adjusted for stratification by clinical site. Baseline value will be an additional covariate for all analyses of change from baseline scores. Consistent with the description of the primary analysis in the protocol, analyses of primary and secondary outcomes will also include an independent variable for study visit. For analysis of measures assessed at multiple time points (for example, C1 and C6), longitudinal modeling will be used and the interaction between time and treatment groups will be included. Unless otherwise noted, all analyses of continuous efficacy variables (e.g., ESS and QOL scales) will be performed using general linear mixed models. Variables with distributions substantially different from normal will be transformed prior to analysis.

Models will be adjusted for pooled clinical site. If there are not enough patients per clinical site, similar sites will be combined (see Section 7.6)

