Change from baseline in iron (transferrin) saturation, ferritin, hemoglobin, hematocrit, MCV, and MCHC.	Continuous	Lab parameters are analyzed at each site (including at local labs) and entered onto CRFS in the EDC system. Transferrin Saturation is calculated within medidata from Iron and Iron Binding Capacity.

Variable	Type	Definition
		The outcome will then be computed as the difference in value at each post-baseline visit and the value at baseline.
Thrombocytopenia platelet categories	Categorical Normal < 150 K/uL < 100 K/uL < 50 K/uL	Added as additional planned safety presentation at blinded data review meeting. Categorical assessment of thrombocytopenia will be calculated based on all platelets collected post-baseline. A person will be classified into one of the 4 categories based on the lowest recorded post-baseline platelet value. The value of 150 represents the lower normal bound.
Neutropenia neutrophils categories	Categorical Normal < 1.45 K/uL < 1.00 K/uL < 0.50 K/uL	Added as additional planned safety presentation at blinded data review meeting. Categorical assessment of neutropenia will be calculated based on all neutrophils collected post-baseline. A person will be classified into one of the 4 categories based on the lowest recorded post-baseline neutrophil value. The value of 1.45 represents the lower normal bound.
Exploratory Outcomes		
Relapse at 4-weeks post treatment	Dichotomous (Yes/No)	The rate of relapse will be calculated at 4 weeks post-treatment. Relapse is defined as a return of the ESS to the baseline value or greater.
Treatment weeks to 1.0 decrease in ESS	Ordinal Categorical (4, 8, 12, 16, 20, 24, Not obtained)	The time to the first 1.0-unit decrease in ESS will be calculated for each participant by computing the difference between the baseline ESS and the ESS at each study visit and determining the first study visit at which the difference is ≤ -1.0 , or “not obtained” if no visit had an improvement of at least 1.0

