Groups will be compared for the proportion of patients relapsed, requiring no blood or iron, and requiring endoscopic interventions and other yes/no categorical outcomes using logistic regression with adjustment for baseline assessment (ESS score, whether the patient had required a blood transfusion or required an total iron infusion amount of at least 250 mg in the 6 months before the baseline visit, and ESS score, respectively), and study site. If events are rare, exact logistic regression will be used.

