9.5 Exploratory Analysis Methods

Exploratory analyses include estimating the rate of relapse at the 4-week post-treatment follow-up visit, where relapse is defined as a return of the ESS to the baseline value or greater in pomalidomide-treated subjects and estimating the median time after initiation of pomalidomide to obtain a decrease of at least 1.0 in the ESS in pomalidomide-treated compared to placebo subjects. These outcomes will have no statistical testing.

To learn which demographic or biomarkers are predictive of greater response to pomalidomide we will fit generalized linear models to the primary outcome in the pomalidomide treatment group to predict treatment response based on presence of the specific mutations in the endoglin (ENG) or

activin-like kinase (ACVRL1) genes, as well as a set of pre-defined baseline covariates., to include age, gender, and baseline disease severity.

An exploratory analysis will evaluate the correlation of the ESS score and the average daily duration of bleeding from the diary.

An exploratory analysis will also compare groups for total iron taken during the treatment period, combining both oral iron and iron infusions.

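### The relapse rule needs no prior improvement, so it mixes lack of response with loss of response, and the SAP both compares arms on it and says it will not be tested

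*SAP*

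**What the plan says.** SAP 3.2.4 lists relapse as an exploratory outcome at the 4-week post-treatment visit: "relapse is defined as a return of the ESS to the baseline value or greater in pomalidomide (or placebo)-treated subjects". SAP 9.2 makes it a Yes/No variable under the same rule: "Relapse is defined as a return of the ESS to the baseline value or greater". Protocol 4.2.3 and 10.4.11 and SAP 9.5 repeat the rule, although Protocol 10.4.11 and SAP 9.5 mention only pomalidomide-treated subjects.

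None of these places requires an earlier fall in ESS, restricts the denominator to responders, or says how to code a patient who never fell below baseline. The default population is set in SAP 9.1: "All efficacy analyses will be performed on the mITT population, the primary population".

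On use, SAP 9.4 says: "Groups will be compared for the proportion of patients relapsed, requiring no blood or iron, and requiring endoscopic interventions", by logistic regression adjusted for baseline ESS and site. Protocol 10.4.3 says the same. SAP 9.5, after describing relapse and the time to a 1.0-point fall, says: "These outcomes will have no statistical testing".

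Two other items bear on the point. A secondary objective in SAP 3.1.2 reads: "To determine whether a continued response to pomalidomide is evident 4 weeks after treatment discontinuation". The next row of the SAP 9.2 table uses a 1.0-point threshold, "The time to the first 1.0-unit decrease in ESS will be calculated for each participant", but does not link it to relapse.

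**The concern.** Relapse normally means losing something gained. Under the written rule the code depends only on the baseline and post-treatment scores. What happened on treatment does not enter. A patient who did not respond and a patient who responded and then lost the response both get Yes.

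This has two consequences. An arm with less response collects more relapses even if nobody loses ground after stopping. Conversely, an effective drug whose whole advantage vanishes after stopping can show the same relapse rate as placebo. Adjusting for baseline ESS, as SAP 9.4 plans, adjusts for initial severity and not for on-treatment response.

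Separately, a reader of the SAP cannot tell whether a between-arm odds ratio for relapse will be produced.

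**Working it through.** The documents state no relapse rate or power for this outcome, so there is no figure to reproduce. The check is a reading of the rule plus an illustration.

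**Inputs**
- SD of ESS change 1.7 (Protocol 10.5).
- Correlation between post-baseline visits 0.5 (Protocol 10.5); 0.7 is an added assumption.
- Placebo mean change -1.5: the 12-week average across all arms of the earlier nasal-spray trial (Protocol 10.5).
- Pomalidomide mean change -2.5: -1.5 plus the design difference of 1.0.
- Alternative post-treatment mean -1.0: the same trial, 12 weeks after treatment stopped (Protocol Table 6).

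**Model.** Six treatment visits and the end-of-study (EOS) visit, multivariate normal with equal correlation, 500,000 simulated patients per setting. Relapse as written is an EOS change of 0 or more.

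**Step 1: rate under the written rule.** P(relapse) = Φ(mean EOS change / SD).
- EOS mean -1.5: Φ(-1.5/1.7) = Φ(-0.882) = 18.9%.
- EOS mean -2.5: Φ(-2.5/1.7) = Φ(-1.471) = 7.1%.
- EOS mean -1.0: Φ(-1.0/1.7) = Φ(-0.588) = 27.8%.

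Neither the week-24 mean nor the correlation appears in the formula. Two arms with the same EOS mean and SD get the same rate, whatever they gained on treatment.

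**Step 2: who is counted.** Ranges run across correlations 0.5 and 0.7.

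| Mean change, week 24 then EOS | Relapsed as written | Of these, at or above baseline at week 24 | Of these, no 1.0 drop at week 24 | Of these, never below baseline at any treatment visit |
|---|---|---|---|---|
| Placebo -1.5, -1.5 | 19% | 42-56% | 68-82% | 7-19% |
| Pomalidomide -2.5, -2.5 | 7% | 28-43% | 53-72% | 2-10% |
| Pomalidomide -2.5, -1.5 | 19% | 20-27% | 43-55% | 1-4% |

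**Step 3: rate among week-24 responders (drop of at least 1.0).** Rate = P(relapse) × (1 - share with no 1.0 drop) / P(week-24 change of -1.0 or lower). The divisor is Φ(0.5/1.7) = 0.616 for placebo and Φ(1.5/1.7) = 0.811 for pomalidomide.
- Placebo -1.5, -1.5: 0.189 × (1 - 0.678) / 0.616 = 9.9% at correlation 0.5; 0.189 × (1 - 0.817) / 0.616 = 5.6% at 0.7.
- Pomalidomide -2.5, -2.5: 0.071 × (1 - 0.532) / 0.811 = 4.1%; 0.070 × (1 - 0.719) / 0.811 = 2.4%.
- Pomalidomide -2.5, -1.5: 0.189 × (1 - 0.430) / 0.811 = 13.3%; 0.189 × (1 - 0.553) / 0.811 = 10.4%.

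The informative case is the first against the third. The written rule gives 19% and 19%; responders show 6-10% and 10-13%. The pattern is the same if both arms drift to -1.0 after stopping: about 28% in each arm as written, against 11-17% (placebo) and 18-21% (pomalidomide) among responders.

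The model ignores the discreteness of the ESS. Exact ties with baseline, which the rule counts as relapse, would add further patients without improvement.

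**The case against.** A reader might infer that most patients counted as relapsed never improved. The figures do not support that. The 68-82% is the share short of a 1.0-point drop at a single visit, so a patient down 0.9 is included. Only about 7-19% of placebo relapses were never below baseline at any treatment visit.

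A reader might also infer that the variable merely repeats the week-24 result. It does not. When pomalidomide goes from -2.5 to -1.5 after stopping, its rate rises from 7% to 19%, and at correlation 0.5 about 80% of those counted were below baseline at week 24 (1 - 0.202). The rule responds to loss of response but cannot separate it from lack of response.

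It can fairly be said that the word return presupposes an earlier departure, and that a denominator of all patients is inferred from the mITT default rather than written into the relapse row. That is so, but nothing makes the implied condition operational, and a programmer coding the Yes/No variable would compare two scores.

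The secondary objective on continued response does not rest on this outcome. Change in ESS at the post-treatment visit is a listed secondary outcome, estimated in the primary repeated-measures model (SAP 3.2.3 and 9.3). Relapse lies outside the alpha-controlled tests in SAP 7.7. These points limit the importance and stand.

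Finally, restricting to responders is not a cure. With no average loss of response in either arm, responders still show 6-10% on placebo and 2-4% on pomalidomide, and responder status arises after randomisation. This is why the restricted rate should be descriptive.

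**Conclusion.** The point holds as a gap in the definition together with a contradiction about use. As written, the rule counts non-improvers as relapsed. Under the planning values, roughly half of placebo relapses (42-56%) were already at or above baseline at week 24. The rule can show a 12-point gap (19% against 7%) with no average loss of response in either arm, and no gap when the drug's whole advantage is lost. SAP 9.4 and 9.5 cannot both be followed for this outcome.

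The sizes are illustrative. They rest on normality, an SD of 1.7, an equal correlation of 0.5 or 0.7 across visits, and means borrowed from a 12-week trial of other treatments plus the design difference. The reading of the rule and the conflict between sections depend on none of these. Severity is low, because the outcome is exploratory and the post-treatment ESS change from the repeated-measures model remains the main evidence on continued response.

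**What to change.** 1. In SAP 9.2, define relapse as EOS ESS at or above baseline among patients who had improved at their last treatment-cycle visit. That is week 24 or, for early stoppers, the visit closing the cycle in which they stopped (Protocol 7.3.5). Requiring a week-24 score would silently drop early stoppers.
2. Use the 1.0-point decrease already in SAP 9.2 as the improvement cut, with any decrease below baseline as a sensitivity cut. The choice should be stated as such, since the protocol also cites a minimally important difference of 0.7.
3. List non-improvers separately by arm.
4. Report within arm, descriptively, with a note that responder status is post-randomisation and that arm differences are not a randomised comparison of durability.
5. Delete relapse from the logistic regression comparison in SAP 9.4 and Protocol 10.4.3, to agree with SAP 9.5.
6. While editing, say how the 20 participants with 12-week follow-up enter this 4-week outcome; SAP 9.3 settles that only for the ESS model.

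The cost is wording and a smaller denominator. No new data are needed.

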9.3 Primary Analysis Methods

For the primary analysis, the change from baseline in epistaxis severity score after 24 weeks of study drug administration will be compared between the pomalidomide and placebo groups using a longitudinal general linear model, often referred to as a mixed model for repeated measures (MMRM) (Davis SM 2014), using the MITT population.

The observed change from baseline score at each scheduled post-baseline visit (Weeks 4, 8, 12, 16, 20, and 24 and 4-weeks post-treatment) is the dependent variable. For the purposes of this analysis, study visit will be treated as a categorical repeated measure. The model will include fixed effects for treatment group, study visit, and interactions between those variables and will include the baseline ESS score as a covariate. The model will also be adjusted for the design effect of stratification by pooled site. A heterogeneous Toeplitz covariance pattern will estimate the variance-covariance of the

within-subject repeated measures (study visit), and the Kenward-Roger method will be used to calculate denominator degrees of freedom. Estimates, p-values and 95% confidence intervals will be presented for treatment group comparisons at each visit. In an intent-to-treat fashion, all data will be included in the primary model, regardless of the treatment actually taken by the patient.

The 20 patients with 12-week post-treatment assessments will be included with all 4-week post-treatment assessments.

Treatment group comparisons of the change in ESS score averaged over the week 16, 20, and 24-week visit assessments (a secondary outcome) will be assessed via estimate and contrast statements within this model.

Sample SAS code for the primary model is as follows:

```
proc mixed covtest;
  where VISIT in ("C1","C2","C3","C4","C5","C6","EOS");
  class subject sitenum trtgp VISIT;
  model DELTA_ESS = ESS_BL sitenum trtgp VISIT trtgp*VISIT / ddfm=kenwardroger;
  repeated VISIT / subject=subject type=toeph R rcorr;
  title "Mixed model for change from baseline ESS";
  lsmeans trtgp*VISIT / cl pdiff=all;
run;
```

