3.2 Outcomes

3.2.1 Primary Outcomes

The primary endpoint of this study is change of the Epistaxis Severity Score from baseline to week 24 in the placebo and pomalidomide-treated groups. The ESS at baseline and each follow-up visit will reflect the patient's symptoms and bleeding over the previous 4 weeks.

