Patients will be seen every four weeks during the study (visits C1-C6 at weeks 4, 8, 12, 16, 20, 24 and 4-weeks post treatment follow-up) to measure the ESS (with 4-week recall, see **Appendix 1**), measure iron stores, and obtain laboratory studies, which will include CBC, metabolic profile, and iron studies. The iron replete state will be defined as a ferritin ≥ 50 ng/ml and a transferrin saturation $\geq 30\%$ (since ferritin levels may be elevated due to concurrent inflammation). Investigators will be encouraged to replete iron stores in patients in both arms of the study based on these parameters, and the amount of iron infused (in mg) recorded. There is no mandate for the use of a particular iron preparation. Investigators will be encouraged to use iron infusions prior to blood transfusion, though the latter will be mandated for a hemoglobin below 6.5 gm/dl and recorded as units of packed red blood cells administered. Blood transfusion may also be given at the investigator's discretion based on symptoms that may include shortness of breath, severe fatigue, or other cardiovascular manifestations. Patients will be assessed for adverse events (AE) throughout the study. Treatment dosage may be reduced, or temporarily or permanently discontinued following AE-specific guidelines related to fatigue, cytopenia, or other toxicities.

The 4-week diary of epistaxis events (see **Appendix 2**) will be recorded at selected intervals between visits throughout the study (weeks 8-12 and 20-24 as well as 0-4 weeks post treatment follow-up). The diary was collected from participants via a phone app developed by RTI available for all smart phones, or as a paper diary for participants without access to a smartphone.

The effect of pomalidomide on QOL will be assessed at the baseline visit, at the 12- and 24-week visits, and at the 4-week post-treatment follow-up visit using validated NIH instruments of 1) NeuroQoL satisfaction with social roles and activities, 2) PROMIS emotional distress – depression, and 3) PROMIS fatigue. We will also assess responses to an HHT specific questionnaire developed specifically for this study and shown to correlate with these PROMIS items. The effect of pomalidomide on duration of epistaxis will be assessed at the 12 and 24-week treatment visits and at the 4-week post-treatment follow up visit.

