4.5 Study Flow Chart of Assessments and Evaluations

Visit	Screen and Baseline		Treatment Period						End of Study	
	SC	BL	C1	C2	C3	C4	C5	C6	EOS	ET
Study Procedures	Week -4 to -8	Week 0	Week 4 0-5 Days	Week 8 0-5 Days	Week 12 0-5 Days	Week 16 0-5 Days	Week 20 0-5 Days	Week 24 0-5 Days	Week 28 (4 week follow up) 0-7 Days	Only for withdrawn consent
Informed Consent	X									
Enrollment Criteria	X									
Demographics	X									
Medical History	X									
Concomitant Medications	X	X	X	X	X	X	X	X	X	X
Physical Exam	X	X ^{1*}	X ¹	X ¹	X	X ¹	X ¹	X	X	X
Vital Signs ²	X	X	X	X	X	X	X	X	X	X
Genetic Testing ³		X								
Iron Infusion	X ⁴	X	X	X	X	X	X	X	X	X
Blood Transfusion	X ⁴	X	X	X	X	X	X	X	X	X
Adverse Events		X	X	X	X	X	X	X	X	X
ESS	X ⁵	X	X	X	X	X	X	X	X ⁵	X
Epistaxis Duration Diary	X	X ⁶		X	X ⁶		X	X ⁶	X ⁶	
CBC with differential	X	X	X	X	X	X	X	X	X	X
CMP	X	X	X	X	X	X	X	X		X
Iron Studies ⁷	X	X	X	X	X	X	X	X	X	X

Visit	Screen and Baseline		Treatment Period						End of Study	
	SC	BL	C1	C2	C3	C4	C5	C6	EOS	ET
Study Procedures	Week -4 to -8	Week 0	Week 4 0-5 Days	Week 8 0-5 Days	Week 12 0-5 Days	Week 16 0-5 Days	Week 20 0-5 Days	Week 24 0-5 Days	Week 28 (4 week follow up) 0-7 Days	Only for withdrawn consent
INR and aPTT	X									
Biorepository Collection	X ⁸	X ^{8*}			X ⁸			X	X ⁸	X
QOL ⁹ surveys		X			X			X	X	X
Pregnancy Testing ¹⁰	X	X	X	X	X	X	X	X		
Randomization		X								
Drug Dispensation		X	X	X	X	X	X			
Drug Return			X ¹¹	X ¹¹	X	X ¹¹	X ¹¹	X		X

SC = Screening; BL = Baseline; C = End of cycle; ESS = Epistaxis severity score; CBC = Complete blood count; CMP = Complete metabolic panel; EOS = End of study Visit; ET = Early termination; QOL = Quality of life; Gray shaded boxes denote flexibility to perform visits remotely in which case physical exam may be modified; vital signs and biorepository samples may not be collected.

¹ Limited physical examination; *A detailed physical exam if screening visit was remote.

² Vital signs will include body weight, blood pressure, pulse and O₂ saturation.

³ Genetic testing will be performed only if not done previously and consent is obtained.

⁴ Information on Iron infusion and Blood transfusion over the past 6 months to be collected at screening visit.

⁵ ESS will be a 3-month recall for these visits; for all other visits, it will be a 4-week recall.

⁶ Epistaxis Duration Diary will be collected at these visits and if applicable a new diary will be dispensed for the next recording.

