7.3 Handling of Dropouts and Missing Data

Missing data and missed visits will be monitored in real-time. In the event a scheduled visit is missed, site coordinators will contact the patient before the follow-up window closes to encourage them to at least obtain measurements relevant to the primary endpoint. For any missing data that do occur, we will record and describe the reasons the data are missing when reporting results.

In the event that one or more ESS or QOL visit assessments is missing during the treatment or post-treatment periods, the MMRM analysis approach which assumes data are missing at random (MAR) will be used to compare treatments based on the available data and the correlation between observations within a person. To guard against bias if the MAR assumption is incorrect, missing data mechanisms will be explored, and sensitivity analyses will be conducted on the primary outcome to assess the robustness of the primary analysis (see Section 9.3.1). Sensitivity analyses are not planned for secondary analyses.

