9.3.1 Sensitivity Analyses

Per-protocol population

The primary analysis will be repeated on the per-protocol population.

Imbalanced covariates

If there are important baseline characteristics that substantially differ between randomized treatment groups by chance, additional sensitivity analyses may be conducted to evaluate the impact of adjusting for those imbalances.

Clinical Site Effects

We will examine descriptively whether the treatment effect varies across sites.

Removing 12-week post-treatment data

A supportive analysis of the 4-week post-treatment assessment time will be completed for the MITT population with removal of the 20 patient visits that were conducted at 12 weeks post-treatment.

Missing data

The MMRM analysis approach assumes missing data due to missed visits or early study discontinuations are missing at random (MAR). If a statistically significant difference between treatment groups is observed in the primary analysis, then a sensitivity analysis will be conducted on the primary outcome to assess the robustness of the primary analysis to the MAR assumption using methods that assume that data are missing not at random (MNAR). Specifically, we will use multiple imputation of missing data to generate multiple imputed complete datasets (no missing data through 24 weeks), conduct analysis of covariance for change from baseline at 24 weeks on each dataset (model change from baseline at 24 weeks = baseline value + site + treatment group), and use Rubin's rule to combine results across the imputed datasets to obtain a comparison of treatment groups (Ratitch, 2014). We will explore 2 sensitivity analyses: (a) impute missing outcomes in the

pomalidomide treatment group (and the placebo group) based on data from the placebo group (control-based imputation), and (b) impute missing outcomes in the pomalidomide group at varying percentages of the observed values (while imputing missing placebo data based on observed placebo values) until a statistically significant treatment group difference is no longer identified (tipping point analysis) (O'Kelly and Ratitch, 2014). These sensitivity analyses will only be conducted if the primary analysis identifies a statistically significant treatment group difference at 24 weeks in the MITT population.

Intercurrent concomitant therapy

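### The main ESS estimate labelled 4 weeks post-treatment includes 20 assessments made at 12 weeks, and the SAP contradicts itself on the ESS recall period at that visit

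*SAP*

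**What the plan says.** Secondary objective 3 in SAP 3.1.2 reads: "To determine whether a continued response to pomalidomide is evident 4 weeks after treatment discontinuation". Follow-up was shortened from 12 weeks to 4 weeks in Protocol version 2.8, and SAP 3.2.4 records the consequence: "Prior to the change, 20 participants had completed the 12-week rather than 4-week follow-up".

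SAP 9.3 handles these visits as follows: "The 20 patients with 12-week post-treatment assessments will be included with all 4-week post-treatment assessments". The sample code has one EOS level of VISIT, so both off-drug times share one mean. Protocol 10.4.2 lists this visit as 4 weeks post-treatment and does not mention pooling.

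SAP 9.3.1 adds a supportive analysis of the 4-week post-treatment time in the MITT population, "with removal of the 20 patient visits that were conducted at 12 weeks post-treatment".

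On recall, footnote 5 of the SAP 4.5 schedule is attached to the ESS at screening and at EOS: "ESS will be a 3-month recall for these visits; for all other visits, it will be a 4-week recall". SAP 3.2.1 says otherwise: "The ESS at baseline and each follow-up visit will reflect the patient's symptoms and bleeding over the previous 4 weeks".

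**The concern.** The objective names a time point, 4 weeks off drug. The estimate carrying that label includes patients who had been off drug three times as long. If response fades after stopping, the 12-week records pull the reported value toward loss of response. The analysis that matches the objective is only supportive for the ESS. For the post-treatment Neuro-QoL, HHT-QOL and PROMIS scores and for relapse it is not stated at all, although these results belong to the same visit.

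The recall footnote raises a second question. Baseline ESS uses a 4-week recall. An EOS score with a 3-month recall would not be comparable with it, and both the change score and the relapse definition compare EOS with baseline. At a true 4-week visit, such a recall would also reach back into weeks on drug.

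**Working it through.** **1. Share of EOS records.** The number of patients with an EOS assessment is not given. The SAP 7.6 site list sums to 24 + 51 + 21 + 16 + 12 + 21 = 145, taken here as the upper limit. The rows for 130 and 102 assume that 10% and 30% of the 145 have no EOS record; these percentages are the discontinuation rates used in Protocol 10.5. (Against the planned 159, the share would be 12.6%.)

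Formulas: share w = 20/N; pooled between-arm difference = (1 − w) × d4 + w × d12; ratio of standard errors after removal = √(N/(N − 20)). For scale, d4 = 1.0, the planning difference, and d12 is assumed to be 0.5 or 0. The 20 are assumed to carry the same weight in both arms.

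| N with EOS | w | Pooled, d12 = 0.5 | Pooled, d12 = 0 | SE ratio |
|---|---|---|---|---|
| 145 | 13.8% | 0.93 | 0.86 | 1.077 |
| 130 | 15.4% | 0.92 | 0.85 | 1.087 |
| 102 | 19.6% | 0.90 | 0.80 | 1.115 |

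Only the 20 stated visits are counted. SAP 3.2.4 also recodes some early termination visits to EOS when more than 28 days had passed, with no upper limit stated.

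**2. Shift in the pooled mean.** Protocol Table 6 gives two before-and-after figures over about 12 weeks off treatment: −1.5 to −1.0 in the large nasal-spray trial, and apparently −4.4 to −3.3 in a thalidomide series of 7 (the table is broken there). If loss is linear, the part between weeks 4 and 12 is 0.5 × 8/12 = 0.33 and 1.1 × 8/12 = 0.73. Multiplied by 0.138, the EOS mean shifts by 0.046 to 0.10 ESS points.

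**3. Relapse, as an illustration.** Relapse is a return to the baseline ESS or above. Assume SD 1.7 and a mean change of −2.0 at 4 weeks and −1.3 at 12 weeks. Then Φ(−2.0/1.7) = 12.0% and Φ(−1.3/1.7) = 22.2%. Pooled: 0.862 × 12.0% + 0.138 × 22.2% = 13.4%. With the smaller fade of 0.33 the pooled rate is about 12.6%.

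**4. Recall, side by side.**
- 3 months at EOS: SAP 4.5, footnote 5 only.
- 4 weeks at follow-up visits: SAP 3.2.1; SAP 4.1, whose visit list includes the post-treatment visit; the form printed in SAP Appendix 1; Protocol 4.2.1; Protocol 7.1.1.1; and the Protocol 7.3.7 schedule, which attaches the 3-month footnote to screening alone.

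If a 3-month (13-week) recall had been used at a visit 4 weeks off drug, 4/13 = 31% of the window would be off drug and 9/13 = 69% on drug. With a 4-week recall, all of it is off drug. The documents do not say which recall was used at the 20 twelve-week visits.

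**The case against.** The strongest reply is that the pooling is open and already answered. The SAP explains how it arose, states the handling, and plans an ESS analysis without the 20 visits, so a clean ESS estimate will exist. This stands in part: the information will be available, but the result carrying the objective's label will be the mixed one, and no such run is stated for the other outcomes at that visit.

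The reply is also right that little hangs on EOS for inference. Week 24 is the primary and key timepoint. SAP 7.7 does not judge other secondary results for significance, and SAP 9.5 plans no testing of relapse. The fade figures are weak too. The nasal-spray figures pool groups that did not differ from placebo, with N falling from 105 to 83, so they say little about a between-arm difference.

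Four stronger readings are tempting, and the documents do not support them:
- **Mixed recall windows were used.** One schedule footnote says 3 months; every other statement says 4 weeks. A leftover from the 12-week follow-up is plausible, though that is an inference.
- **The SAP rules out any such run for secondary outcomes.** SAP 7.3 says "Sensitivity analyses are not planned for secondary analyses", but in the context of missing data. Post-treatment ESS is itself a secondary outcome and has a supportive run. The SAP is silent on the other outcomes; it does not forbid the run.
- **The diary outcome is mixed as well.** SAP 3.2.2 defines its post-treatment window as weeks 1–4, whatever the date of the visit.
- **The week-24 result is compromised.** EOS data could touch it only indirectly, through the shared covariance model.

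**Conclusion.** The point holds in a limited form. The main ESS estimate labelled 4 weeks post-treatment includes 20 records from 12 weeks, at least 13.8% of the total if no more than 145 patients have an EOS assessment. The matching analysis is supportive for the ESS and unstated for the post-treatment quality-of-life scores and relapse. The expected effect is small: 0.05 to 0.10 ESS points on the mean, assuming linear loss and the Table 6 figures, against an SD of 1.7 and a minimal important difference of 0.7. In the more adverse case of a between-arm difference that has vanished by 12 weeks, 1.0 would be reported as 0.80 to 0.86. The direction of any bias in the between-arm contrast is an assumption.

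The recall footnote is a separate contradiction to be settled from the CRF. These results are descriptive, so the label is much of what the reader takes away, and it should be correct.

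**What to change.** - **SAP 9.3 and 9.3.1:** for every result labelled 4 weeks post-treatment (ESS, Neuro-QoL, HHT-QOL, PROMIS, relapse), make the main analysis the one that sets the 20 twelve-week EOS records to missing and keeps those patients' C1–C6 data. Report the pooled version as supportive.
- **Primary model:** do not add a separate 12-week visit level. It would add covariance parameters to the heterogeneous Toeplitz structure behind the week-24 test, for only 20 patients.
- **Diary:** state that only entries from post-treatment weeks 1–4 are used.
- **SAP 4.5:** remove footnote 5 from the EOS ESS, confirm on the CRF which recall was used, including at the 20 visits, and flag any EOS ESS taken with a 3-month recall.

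The cost is a wording change, a recoded visit flag and a CRF check, best done before unmasking. Precision at EOS falls: the standard error rises by about 8% if 145 patients have EOS data (145 to 125) and about 12% if 102 do (102 to 82, an assumed number). No new data are needed.
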